A particular concern with unnecessary admissions is that a proportion of patients, particularly those with longer hospital stays, undergo a negative appendicectomy.[3] An unnecessary appendicectomy carries the same rate of complications as surgery for true appendicitis.[4] Complications include wound infections, port site hernias, pain and unnecessary time away from their usual activities, such as work, education and caring.[2,5-6] In the UK, the negative appendicectomy rate (NAR) has consistently been found to be around 20%. This suggests there are up to 15,000 appendicectomies being performed annually for patients with a normal appendix. Hence, a large number of patients are exposed to harm from postoperative complications (7% of women and 23% of men).[2] In comparison to other European countries, the UK has a three-fold higher rate of unnecessary operations for appendicitis.[2]

Standardisation of pathways in right iliac fossa pain

There is significant variation in UK practice in the management of RIF pain, which leads to inappropriate selection of patients for imaging and surgery and results in suboptimal patient outcomes.[2-3] Our goal is to use education to standardise practice and encourage risk stratification and selective imaging in RIF pain. Evidence-based recommendations for diagnosing appendicitis exist but many healthcare professionals are not aware of them and they are rarely implemented in practice. Our primary intervention is an evidence-based programme to improve diagnostic assessment in suspected appendicitis. We also assess the effectiveness of the CLARITY implementation strategies in the emergency setting.

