CLARITY is a multicentre, parallel cluster randomised controlled trial with a hybrid type II effectiveness-implementation design. This will assess both the implementation and effectiveness of our intervention. Our primary intervention is the evidence-based programme to improve diagnostic assessment in suspected appendicitis. However, we also assess the effectiveness of the CLARITY implementation strategies. Studying implementation strategies tailored to acute surgical teams is crucial to increasing the adoption of practice-changing interventions in emergency surgery.

CLARITY involves healthcare staff at the level of the hospital, not individual patients. Therefore, a cluster randomised trial is the most appropriate design (figure 1). We will study whether undertaking the CLARITY intervention increases the adoption of best-practice recommendations and whether this leads to an improvement in patient outcomes.

[figure not shown]
RESEARCH QUESTION

Can implementation of an evidence-based educational intervention, focused on the accurate diagnosis of acute appendicitis, safely reduce unnecessary admissions to hospital in patients with suspected appendicitis?

Trial design

The CLARITY trial is a multicentre, cluster randomised controlled trial using a hybrid type II implementation effectiveness design. Sites will be randomised using a 1:1 minimisation algorithm into three batches with a staggered start (see figure 2). CLARITY includes an internal pilot study.

Figure 2: Parallel cluster randomisation with staggering of sites across three start dates. Groups A+B are part of the internal pilot and include roughly 10 sites. The remaining groups will contain at least another 30 sites between them.

TRIAL OBJECTIVES

Pilot study objectives

We aim to conduct a pilot study assessing the feasibility of a full phase trial, measured by site recruitment, uptake of our intervention and collection of primary outcome data. This includes the following objectives:

- Open at least 9 sites, with a mix of rural, district general and tertiary centres
- Accrual of data from a minimum of 100 patients over 8 weeks
- Sufficient uptake of the intervention by local participants

Main trial objectives

 To determine whether implementation of the CLARITY evidence-based programme can reduce non-operative admission rates

Secondary objectives

- To determine whether implementation of the CLARITY evidence-based programme can reduce unnecessary surgeries and improve patient outcomes

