The primary outcome measure is the proportion of people admitted overnight with right iliac fossa pain, who do not undergo an operation. This is known as the non-operative admission rate (NOAR). A small minority of non-operative admissions on the suspected appendicitis pathways will be due to other acute GI pathologies treated by the general surgical team (e.g. diverticulitis, colitis, hepatobiliary, tumours of the appendix, small bowel or colon etc.). Furthermore, a few patients with simple appendicitis may be managed nonoperatively. According to RIFT study, these groups constitute around 3% of all RIF pain referrals. Our objective is to reduce the NOAR while accepting that a very small number of nonoperative admissions will remain necessary. We will measure the contribution of these groups to non-operative admissions.

Main Trial Secondary Outcome Measure

The secondary outcomes will describe the efficacy and safety of the CLARITY package. Of primary concern is safety, as the CLARITY trial seeks to test whether the EBP can reduce unnecessary appendicectomy, whilst maintaining safety. All outcomes in the main study should be measured up to 30 days from attendance/admission, with day 0 being the first day of attendance/admission.

The secondary safety outcomes will include:

- Proportion of patients that were not correctly diagnosed with appendicitis on their first hospital attendance and review by the surgical team (missed or delayed diagnosis)
- The proportion of patients with complicated appendicitis (phlegmon, abscess or perforation)

Version 1.0, Jan 7, 2024

- Days alive and out of hospital
- Readmission or re-attendance to hospital (including discharge from assessment unit and subsequent reattendance for appendicitis i.e. 'missed appendicitis')
- Radiological, percutaneous or endoscopic drainage
- Unplanned admission to critical care (Level 2/3 care)
- Mortality (both inpatient and in the community from any cause)

The secondary safety outcomes for patients who received an operation are:

- Proportion of patients with a negative appendicectomy (appendix normal on histopathological examination)
- Time from symptom onset to decision to operate and to skin incision (in hours)
- Surgical site infection, as defined by the Centers for Disease Control criteria
- Surgical complications, as measured using the Clavien-Dindo classification system
- Reoperation for any cause

CLARITY CHAMPIONS AND TRAINING

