Analyses will be conducted on an intention-to-treat basis (i.e. all patients recorded in the database during the scheduled 8-week recruitment periods will be included). We will compile a full statistical analysis plan prior to data analysis. This trial will be reported according to the CONSORT guidelines, the CONSORT cluster RCT extension and the Standards for Reporting Implementation Studies (StaRI) statement.

Statistical analysis

All analyses will be performed with respect to the clustered nature of the data. Summary data will be tabulated using simple counts and percentages for categorical data. Where continuous data are normally distributed, the mean average will be presented alongside the standard deviation. Where data are not normally distributed, the median average will be presented alongside the 25th and 75th percentiles. Given randomisation, we will not formally test for differences in the characteristics of patients included in different clusters.

All data will be checked and data quality rules will be implemented to ensure data included in analyses are accurate. Missing covariate data will be fully reported and the reason for missingness established. Where possible, centres will be asked to supply the missing data, however, if this is not possible, we will perform multiple imputation when there is a significant amount of missing data (>10%). For missing outcome data, we will perform a best/worst case scenario analysis by imputing missing values with extreme values to assess whether missing outcome data is likely to impact our findings.

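### Surgical complications and negative appendicectomy are compared only among operated patients, a group the package is meant to change, so complications avoided by not operating cannot show

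*Protocol*

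**What the plan says.** The Protocol, under Main Trial Secondary Outcome Measure, splits the secondary outcomes into two lists. The first has seven outcomes and no restriction by operation: missed or delayed diagnosis, complicated appendicitis, days alive and out of hospital, readmission or re-attendance, drainage, unplanned critical care and mortality. The second opens with "The secondary safety outcomes for patients who received an operation are". It contains "Proportion of patients with a negative appendicectomy (appendix normal on histopathological examination)", times to the decision to operate and to incision, surgical site infection, "Surgical complications, as measured using the Clavien-Dindo classification system", and reoperation.

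The same section says that "the CLARITY trial seeks to test whether the EBP can reduce unnecessary appendicectomy, whilst maintaining safety". The secondary objective is to find out whether the programme "can reduce unnecessary surgeries and improve patient outcomes". So the trial intends to change who is operated on.

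The Statistical Analysis Plan section of the Protocol describes intention to treat, in that "all patients recorded in the database during the scheduled 8-week recruitment periods will be included". It defines no all-patient version of the outcomes in the second list. Two statements in Background and Rationale matter here: "the negative appendicectomy rate (NAR) has consistently been found to be around 20"%, and "An unnecessary appendicectomy carries the same rate of complications as surgery for true appendicitis".

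**The concern.** Being operated on happens after randomisation and lies on the path by which the package is meant to work. If the package spares some patients an unnecessary operation, those patients drop out of the denominator for infection, complications and reoperation. The remaining operated patients are selected differently in the two arms, so the comparison loses the protection of randomisation. The covariate adjustment, and the matching for rare events, in the Statistical analysis section are not aimed at this selection.

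The Background gives harm from unnecessary appendicectomy as a reason for the trial. A comparison that removes the spared patients from view cannot show that this harm was avoided.

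**Working it through.** The plan gives no sample size, power or expected effect for these outcomes. Its power of 0.90 is for the primary outcome and does not bear on this point. The check is therefore arithmetic on denominators.

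**Inputs**
- Attendees per arm: 20 clusters × 120 = 2400 (Protocol, Sample Size).
- Negative share of operations in control, q = 0.20 (Background).
- Complication risk c, the same after negative and true operations (Background). The value is assumed to be 10%; it cancels from the ratios.
- Share of attendees operated in control: not given. 30% is assumed, with 20% and 40% as a range.
- a = share of negative operations avoided; b = share of true-appendicitis operations avoided. Both are assumptions.

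**Formulas**
- Ratio of operations, intervention to control: R = q(1 − a) + (1 − q)(1 − b).
- Complications with equal risk: per operation c/c = 1; per attendee R.
- Negative appendicectomy: per operation (1 − a)/R; per attendee 1 − a.

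The operated share appears in none of these ratios.

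**1. Complications, intended mechanism (a = 0.5, b = 0)**
- R = 0.2 × 0.5 + 0.8 = 0.90. The ratio is 1.00 per operation and 0.90 per attendee.
- In counts: control has 0.30 × 2400 = 720 operations, of which 144 are negative. Intervention has 72 + 576 = 648.
- At c = 10%, the rate per operation is 10.0% in both arms. Per attendee it is 72/2400 = 3.00% against 64.8/2400 = 2.70%.
- With 20% operated, the per-attendee rates are 2.0% and 1.8%; with 40%, 4.0% and 3.6%.
- With a = 0.25, R = 0.15 + 0.8 = 0.95: again 1.00 per operation, and 0.95 per attendee.

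**2. Negative appendicectomy, same mechanism**
- Per operation: 144/720 = 20.0% against 72/648 = 11.1%, ratio 0.5/0.9 = 0.56.
- Per attendee: 144/2400 = 6.0% against 72/2400 = 3.0%, ratio 0.50.
- Both denominators show the benefit.

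**3. Negative appendicectomy when true-appendicitis operations also change**
- Equal falls (a = b = 0.25): 108 negative among 540 operations is still 20.0%, although the per-attendee rate falls from 6.0% to 108/2400 = 4.5%. The benefit is hidden.
- 10% more true operations, negative operations unchanged: 144/(144 + 633.6) = 18.5%, although the per-attendee rate stays at 6.0%. A benefit appears where there is none.

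**4. Complications with unequal risks, contrary to the Background (12% true, 7% negative, both assumed)**
- Control: 576 × 0.12 + 144 × 0.07 = 79.2 events, or 11.00% of 720.
- Intervention: 576 × 0.12 + 72 × 0.07 = 74.16 events, or 11.44% of 648.
- The ratio is 1.04 per operation and 74.16/79.2 = 0.94 per attendee.

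**5. Could the trial detect the per-attendee complication difference?**
- In step 1 it is 3.00% − 2.70% = 0.30 points. The standard error, ignoring clustering, is √[(0.03 × 0.97 + 0.027 × 0.973)/2400] = 0.0048, so z is about 0.6 and power about 10%. Any positive intra-cluster correlation would tend to lower this.

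**The case against.** Several points count against a strong form of this concern.

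- **Apparent harm.** A reader might infer that the operated-only comparison would show more complications in the intervention arm. That needs negative operations to carry lower risk than true ones (step 4), and the Background says the rates are the same. On the Protocol's own premise the ratio is 1.00: the benefit is hidden, not reversed.
- **Negative appendicectomy.** A reader might infer that this outcome also loses its benefit. Under the intended mechanism it does not (step 2; z about 4.6 per operation and 5.0 per attendee, ignoring clustering). Hiding the benefit needs true-appendicitis operations to fall at least as fast as negative ones, and the Protocol expects few patients with simple appendicitis to be managed without surgery. The per-operation rate is also the figure the Background uses to compare countries, so it should stay.
- **Primary outcome.** A reader might infer that the non-operative admission rate is at fault because an admitted patient with a normal appendix removed is a non-event. That follows from its definition, and negative appendicectomy is measured separately. A supportive analysis counting both is optional and does not carry this point.
- **Other outcomes.** The seven unrestricted outcomes can pick up serious harm avoided. This is a real mitigation, but none of them records surgical site infection or graded surgical complications.
- **The full analysis plan.** It is promised and not shown, and could add all-attendee versions. The Protocol's own text nevertheless fixes the operated group.
- **Ascertainment.** Each hospital chooses how to find patients, and clinical teams and assessors know the allocation. Attendees who are not admitted may be easier to miss than theatre cases, so an all-attendee denominator has its own exposure to bias.

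What stands is the core: the analysis group is formed after randomisation, and complications avoided by not operating lie outside it.

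**Conclusion.** The concern holds in limited form. For surgical site infection, complications and reoperation, the stated comparison cannot show events avoided by not operating: 1.00 per operation against 0.90 per attendee. This rests on the Protocol's equal-risk statement and its 20% negative rate, and on the assumption that half of negative operations, and no others, are avoided. It does not depend on the operated share or on the level of complication risk.

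For negative appendicectomy the problem is conditional: the per-operation rate misleads, in either direction, only if operations for true appendicitis also change.

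The practical size is modest. These are secondary outcomes, and on the assumptions above the trial would be unlikely to show the complication difference statistically with either denominator. The gain is an estimate that answers the secondary objective in the groups as randomised. It is worth making because it is cheap.

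**What to change.** - For surgical site infection, Clavien-Dindo complications, reoperation and negative appendicectomy, make all eligible attendees, by randomised arm, the denominator of the between-arm comparison. Count a patient with no operation by day 30 as having no event.
- Report the operation rate by arm, so that a change in who is operated on is visible.
- Keep the per-operation rates alongside, for comparison with published figures. Times to decision and incision exist only for operated patients and stay as they are.

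**Cost.** A change of wording and a few table rows. The data are already to be collected on all attendees to 30 days.

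**Downside.** Per-attendee rates are less familiar, and they depend on complete capture of non-admitted attendees at unblinded sites. They should be read with the case-ascertainment check in the Data validation section. That check covers 10% of centres (about 4 of 40) and is reported pooled, so it gives limited information on any difference between arms.

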This study would not be feasible with individual patient randomisation due to a high risk of bias and contamination between study arms. A cluster randomised trial is the most appropriate study design due to the intervention being implemented at hospital-level. Once the emergency surgical teams have completed the educational module, they will implement a change in practice for all subsequent patients they see.

Individual patient consent for the intervention is not possible, as the intervention is being implemented at hospital-level. Moreover, the intervention is low-risk with no specific risks anticipated. Importantly, in this pragmatic study, the educational e-modules are intended to inform clinical practice and harmonise Version 1.0, Jan 7, 2024

care according to current best clinical practice. Patients in sites allocated to the intervention arm will receive what is deemed to best evidence based care, with no new approaches tested.

Only routinely collected data will be collected in the CLARITY trial. Patients will not undergo any additional investigations for the purposes of this study. Clinical follow-up will be limited to review of health records up to a maximum of 30 days following attendance/admission to hospital. There will be no additional patient contact (telephone or in-person) beyond what is normal clinical practice at each centre. As such, if a patient is discharged from hospital before day 30, and no further routine contact with medical services is made, follow-up will be limited to inpatient care.

We anticipate that most ethics review boards will waive the requirement for patient consent, as only anonymised audit data will be collected. Each centre must, however, gain written approval from their research and development department.

BLINDING

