In the latter phase of data collection, patients who attended or were admitted to hospital with right iliac fossa pain, including those who did not undergo appendicectomy or were found to have alternative cause for their right iliac fossa pain, will be followed up to a maximum of 30 days (with day 0 being the day of attendance/admission) by a review of their inpatient health records, routine clinic visit letters, and reports for postoperative radiological investigations arranged as part of normal patient care. There will be no additional patient contact (telephone or in-person) beyond what is normal clinical practice at each centre. The study is designed so that existing patient follow-up pathways and health records can be used efficiently, with only data that is routinely collected as part of normal clinical care being captured. Appendicitis is unlikely to spontaneously resolve or recur without treatment (surgery or antibiotics), so 30 days should provide an adequate time frame to capture any complications or readmissions.

The CRF on REDCap has been designed to be straightforward and focuses on pertinent data points. In order to ensure the trial has validity, a minimum threshold of 90% data completion across all included patients will be used. Centres who have 90% or higher data completion rates will be included in the trial analysis and all CLARITY team members will be eligible for co-authorship. Centres with data completion below 90% will not be eligible for co-authorship.

Figure 4: Overview of REDCap data collection forms to be completed for the main CLARITY study.

REDCap forms to complete

SAMPLE SIZE

To detect a 25% reduction in the non-operative admission rate, assuming an intra-cluster correlation (ICC) of 0.06 and an α of 0.05, 40 clusters (20 per arm) of 120 patients would be required — 4800 patients in total. This sample size would provide a power of 0.90. We have been conservative in these estimates and factored in a cluster size variation of 50%.

PROJECTED ACCRUAL

Assuming each of the 40 centres sees 20 patients per week with right iliac fossa pain or suspected appendicitis, each centre should have accrued adequate data within 6 weeks of data collection commencing. The data collection period should run for 8 weeks, so there will be adequate time for centres to accrue cases and achieve the expected sample size.

STATISTICAL ANALYSIS PLAN

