DATA HANDLING AND RECORD KEEPING

Source Data

Source data within the CLARITY study will be kept as part of the participants' medical notes generated and maintained at each site. As all data collected and analysed within the CLARITY study are routinely collected, source data will only be within the medical notes or linkage to routinely captured administrative datasets.

Data Management

Information will be collected at the following times:

During the index hospital admission or attendance

• Up to 30 days after the hospital admission or attendance

Data will be entered directly onto the secure electronic CLARITY REDCap database by study collaborators at the participating hospital sites.

Site study collaborators will be provided with a paper copy of the eCRF to facilitate data collection. If this is used, they should transfer data from the paper CRF into the online CLARITY database (https://www.bistc.redcap.bham.ac.uk). CLARITY data management staff will check all incoming data CRFs for completeness, data consistency and compliance with the protocol. If discrepancies or missing data are identified, the CLARITY data management staff will raise queries with the research team at the participating hospital via the CLARITY REDCap database.

Data Security and Data Protection

The security of the Study Database System is governed by the policies of the University of Birmingham. The CLARITY study database will be hosted on the REDCap system managed and maintained by the BiSTC.

Data management and data security within the BiSTC will abide by the requirements of the General Data Protection Regulations (GDPR) and any subsequent amendments. The study will be conducted at collaborating sites in accordance with the country-specific data protection requirements. Data will be acquired and stored on the REDCap platform. Access to data will be restricted with usernames and passwords. Each participant will be allocated a unique study number at entry. All communication will use this as the identifier. All data will be analysed and reported in summary format. No individual will be identifiable in any summary data statistics. Linked data will be analysed within a trusted research environment. In all analyses, patients will remain anonymous.

QUALITY CONTROL AND QUALITY ASSURANCE

Site set-up and initiation

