Patient identifiable information will not be collected in this study (i.e. names or dates of birth). All data for analysis at the University of Birmingham will be anonymised. All data collected about participants will be identified using only a unique CLARITY study number. This number will be automatically allocated via REDCap once a new patient record is created in the CLARITY REDCap database. Any correspondence between the CLARITY study office and hospital sites will use the CLARITY study number only. The linkage between REDCap study ID and participants will be maintained in strict confidence at participating sites. This data will not be submitted to the CLARITY study office and will not be sent outside of the participating site. Confidentiality of all participant's data will be maintained and there will be no disclosure of information by which participants may be identified to any third party other than those directly involved in the treatment of the participant.

INSURANCE AND INDEMNITY

The University of Birmingham has in place Clinical Trials indemnity coverage for this study which provides cover to the University for harm which comes about through the University's, or its staff's, negligence in relation to the design or management of the study.

The risk of the trial is no greater than the risk of the standard clinical care. Responsibility for the participants at sites remains with the organisation responsible for the clinical site and it is therefore indemnified through their normal arrangements.

AUTHORSHIP

The output from this research will be published under a single corporate authorship group: "CLARITY Trial Collaborators". The following roles will be recognised within the collaborating authorship list: Writing group, Protocol group, CLARITY Study Management Group, CLARITY Operations Committee, CLARITY Education Committee, CLARITY Data Management Committee, Study Steering Committee, Data Monitoring Committee, Statistical Analysis, CLARITY co-ordinators, Principal Investigators, co-Principal Investigators, Collaborators.

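### The itemised 30-day record sources cannot systematically capture community death, return to another hospital or days alive and out of hospital, and the protocol contradicts itself on the linkage that might

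*Protocol*

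**What the plan says.** The Protocol, under Main Trial Secondary Outcome Measure, sets a 30-day window for all outcomes and names safety as the main concern among the secondary ones. Its list includes "Mortality (both inpatient and in the community from any cause"), days alive and out of hospital, and readmission or re-attendance. The last expressly covers a patient discharged from the assessment unit who comes back with appendicitis.

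Under Data Collection and Follow-up, the sources are a "review of their inpatient health records, routine clinic visit letters, and reports for postoperative radiological investigations", with no patient contact beyond normal practice. Ethics and Consent describes the source more widely, as health records, and then says of a patient discharged before day 30 that if "no further routine contact with medical services is made, follow-up will be limited to inpatient care". The synopsis speaks of hospital notes.

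On linkage, the Source Data section says that "source data will only be within the medical notes or linkage to routinely captured administrative datasets", and Data Security and Data Protection says that linked data will be analysed in a trusted research environment. Confidentiality and Data Protection says that no identifiable information is collected. Of the key between study number and patient it says: "This data will not be submitted to the CLARITY study office and will not be sent outside of the participating site".

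**The concern.** The research question is whether admissions can be reduced safely. If the intervention works, more patients go home from the emergency department or assessment unit without an overnight stay. For those patients, a missed appendicitis or a death would occur after the index attendance. The itemised sources suit an operated inpatient. A patient sent home on day 0, who is eligible under Patient Identification without being admitted, may have no inpatient record, no clinic letter and no postoperative scan. If such a patient returns to a neighbouring hospital with perforation, or dies at home, no listed source would reliably show it.

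At stake is the safety half of the conclusion. Events that nobody looks for cannot be recovered by analysis, so this cannot be left to a statistical analysis plan.

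**Working it through.** **The plan's own figure.** The only power statement concerns the primary outcome: "40 clusters (20 per arm) of 120 patients would be required — 4800 patients in total", and "This sample size would provide a power of 0.90". With ICC 0.06, 120 patients per cluster and a coefficient of variation of 0.5, the design effect is 1 + ((1 + 0.5²) × 120 − 1) × 0.06 = 9.94. The effective number per arm is 2400 / 9.94 = 241. Taking the control rate as 60% (an assumption from the Background; the sample-size section gives none), a 25% relative reduction to 45% and a two-sided 0.05 test, power is 0.912. The requirement is 19.1 clusters per arm, rounded up to 20, or 4800 patients. The figure reproduces, and nothing below depends on it.

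**Outcome against source.**
- *Community death.* No named source. Some deaths may reach the notes or a letter, but not systematically.
- *Return to another hospital.* No named source, with the same reservation.
- *Days alive and out of hospital.* Needs vital status and every hospital day to day 30, so it inherits both gaps.
- *Return to the same hospital's emergency department or assessment unit.* Covered if hospital notes (synopsis) or health records (Ethics and Consent) are read. Not covered if only inpatient records are read (Data Collection and Follow-up).
- *Linkage.* Foreseen under Source Data, but under Confidentiality and Data Protection neither identifiers nor the key reach the study office.

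**Checks that might close the gap.** Data validation covers case ascertainment in 10% of centres, not follow-up outcomes. The 90% completion threshold concerns whether data are entered, not whether an event was looked for. The best/worst-case analysis acts only on values that are missing.

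**Size under equal capture (assumed; the documents give no rate).** If a proportion c of events is captured in both arms, the observed rate is c × the true rate. Assume true rates of 2.0% v 1.0%:
- c = 0.9: 1.8% v 0.9%, difference 0.9 points, ratio 2.0.
- c = 0.7: 1.4% v 0.7%, difference 0.7 points, ratio 2.0.

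The true difference is 1.0 point, so 1 − c, or 10-30%, of the excess is lost. That proportion is the same at any base rate.

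**Effect on power (assumed 5% v 7.5%, 2400 per arm).** Without clustering, power falls from 0.95 to 0.89 with 20% of events missed and to 0.84 with 30% missed. With an assumed ICC of 0.01 (design effect 1 + 149 × 0.01 = 2.49), it falls from 0.62 to 0.52 and 0.47.

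**Size under unequal capture (assumed).** Observed ratio = true ratio × (1 − missed in intervention) / (1 − missed in control). With a true ratio of 1.5 and 10% missed in control:
- 20% missed in intervention: 1.5 × 0.8 / 0.9 = 1.33.
- 30%: 1.5 × 0.7 / 0.9 = 1.17.
- 40%: 1.5 × 0.6 / 0.9 = 1.00.

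**The case against.** Follow-up from routine records without patient contact is a declared pragmatic choice, and the sentence in Ethics and Consent is an open, conditional statement of its limit. That is fair. It does not supply a source for outcomes that are still listed without qualification.

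Several stronger readings are tempting, and the document does not support them.
- A reader might infer that emergency re-attendance cannot be captured at all. For the same hospital this rests on one word, inpatient, in Data Collection and Follow-up. The wider terms elsewhere would include such visits, and the outcome definition itself tells sites to record them. Data validation also shows that attendance records can be consulted on site. The fault there is inconsistent wording.
- A reader might infer that linkage has been ruled out. It is provided for in one place and made unworkable in another, which is an unresolved contradiction.
- A reader might infer that unseen events are entered as absent, or that community deaths are captured at zero. The case report form is not shown, so the coding of unknown status cannot be checked, and some outside deaths may reach the notes.
- A reader might infer a demonstrated bias towards 'safe'. Equal capture leaves the risk ratio unchanged, so a directional bias requires more missed events in the intervention arm. More discharges make that plausible, but no figure in the document shows it.

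The illustrative 2.0% v 1.0% is also high against the Background, which puts missed diagnoses below 1%. The proportionate loss does not depend on it.

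**Conclusion.** The point holds in limited form. As written, the follow-up cannot systematically capture three listed outcomes: community mortality, return to another hospital, and days alive and out of hospital. The wording on same-hospital returns is inconsistent. Its narrowest reading would miss returns by patients sent home without admission, the group the intervention aims to enlarge. The two sections on linkage conflict.

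At an assumed equal capture of 70-90%, 10-30% of any absolute safety excess would go unseen, with some loss of power and no change in the risk ratio. A false impression of safety in relative terms would require unequal capture, which is possible but not established. The primary outcome, read as overnight stay without operation at the index attendance, is unaffected, as is the sample size. Because the trial asks whether admissions can be reduced safely, the mismatch should be settled before data collection.

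**What to change.** 1. Amend Ethics and Consent and Data Collection and Follow-up so that the day-30 site review covers emergency department, assessment-unit and ambulatory attendance records, and all imaging and histology, at the index hospital. Use one description of the sources throughout, including the synopsis.
2. Treat status that cannot be determined as missing, not as no event, so that the planned best/worst-case analysis applies to it. State that such an entry does not count against a centre's 90% completion threshold; otherwise sites have a reason to enter 'no'.
3. Reconcile the Source Data and Data Security text with Confidentiality and Data Protection: either describe a workable route for linkage or remove it.
4. Unless linkage or another named source is made workable, restate the outcomes as mortality known to the index hospital, return to the index hospital, and days alive and out of the index hospital, and limit the safety conclusion to these.

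The cost is slightly more record review by staff already doing the day-30 check, a protocol amendment, possibly one extra response option on the form, and, under step 4, a narrower safety claim.
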